14. Subjects will collect a pre-dose faeces sample at home in specific containers provided by [REDACTED]
15. Confirmation of fitness includes physical and neurological examination, vital signs, ECG, suicidality assessment (C-SSRS) only at Day 15 and EOT, recordings of AEs and concomitant therapies as well as evaluation of safety laboratory assessed on Day 8.
16. At this time point, only a sample for haematocrit measurement is taken.
17. PCR testing for SARS-CoV-2 will be performed at admission on Day – 1, on Day 2, at each admission to the trial site for the 24-h visits and at EOT.

Proprietary confidential information © 2020 Boehringer Ingelheim International GmbH or one or more of its affiliated companies

Flow Chart: Part 2 (Multiple dose)

Visit	Day	Planned time (relative to drug administration) [h:min]	Approximate clock time of actual day [h:min]	Event and comment	Safety laboratory	PK _{plasma} ^{2,9}	PK _{urine} ⁵	12-lead ECG	Vital signs (BP, PR)	Questioning for AEs & concomitant medication
1	-21 to -2			Screening (SCR) ¹	A			x	x	x
2	-1	-21:00	11:00	Admission to trial site	B ^{10, 11}					x
	1	-2:00	06:00			x ³	x ³	x ³	x ³	
		-0:30	07:30	Standard continental breakfast						
		0:00	08:00	Drug administration						
		0:30	08:30			x				
		1:00	09:00			x				
		2:00	10:00			x				
		4:00	12:00	Lunch ⁶		x				
		5:00	13:00			x				
		6:00	14:00			x				
		7:00	15:00			x				
		8:00	16:00			x				
		10:00	18:00	Dinner ⁶		x				
		12:00	20:00	Snack ⁶		x				
		14:00	22:00			x				
	2	24:00	08:00	Drug administration ¹²	x ¹¹	x ³	x ³			
	3	48:00	08:00	Drug administration ¹²						
	4	72:00	08:00	Drug administration ¹²						
	5	96:00	08:00	Drug administration ¹²						
	6	120:00	08:00	Drug administration ¹²						
	7	144:00	08:00	Drug administration ¹²	B ⁸	x ³	x ³	x ³	x ³	
		144:30	08:30			x				
		145:00	09:00			x				
		146:00	10:00			x				
		148:00	12:00	Lunch ⁶		x				
		149:00	13:00			x				
		150:00	14:00			x				
		151:00	15:00			x				
		152:00	16:00			x				
		154:00	18:00	Dinner ⁶		x				
		156:00	20:00	Snack ⁶		x				
		158:00	22:00			x				
	8	168:00	08:00	Drug administration ¹²		x ³				
	9	192:00	08:00	Drug administration ¹²		x ³	x ³			
	10	216:00	08:00	Drug administration ¹²						
	11	240:00	08:00	Drug administration ¹²		x ³	x ³			
	12	264:00	08:00	Drug administration ¹²						
	13	288:00	08:00	Drug administration ¹²						
	14	312:00	08:00	Drug administration ¹²	B ⁸	x ³	x ³	x ³	x ³	
		312:30	08:30			x				
		313:00	09:00			x				
		314:00	10:00			x				

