Proprietary confidential information © 2020 Boehringer Ingelheim International GmbH or one or more of its affiliated companies

3. The time is approximate; the procedure is to be performed within a time window of 3 h prior to drug administration.
4. Confirmation of fitness includes physical and neurological examination, vital signs, ECG, suicidality assessment (C-SSRS), recordings of AEs and concomitant therapies as well as evaluation of safety laboratory assessed on Day 21.
5. Urine collection (for PK assessment [REDACTED] planned time): A predose urine sample collected and stored on Day -1 or Day 1 predose will serve as blank sample. Urine collection is to be performed as described in the [Flow Chart](#).
6. If several actions are indicated at the same time point, the intake of meals will be the last action.
7. End-of-trial (EOT) examination includes physical examination, vital signs, ECG, safety laboratory, recording of AEs and concomitant therapies, neurological examination and suicidality assessment (C-SSRS). The EOT assessments will be performed after the last PK sample on Day 62 has been taken.
8. Subjects are to be fasted for at least 10 h before sample is taken.
9. For definition of the individual subject's end of trial see Section [6.2.3](#)
10. Urine drug and alcohol screening will be done at this time point.
11. PCR testing for SARS-CoV-2 will be performed at admission on Day – 1, on Day 2 and at EOT.
12. A standard continental breakfast will be provided approx. 30 min prior to each daily drug administration from Day 1 to Day 21.

TABLE OF CONTENTS

TITLE PAGE	1
CLINICAL TRIAL PROTOCOL SYNOPSIS	2
FLOW CHART	5
TABLE OF CONTENTS	11
ABBREVIATIONS	15
1. INTRODUCTION.....	18
1.1 MEDICAL BACKGROUND	18
1.2 DRUG PROFILE	19
1.2.1 BI 1358894	19
1.2.2 Residual Effect Period	22
1.3 RATIONALE FOR PERFORMING THE TRIAL	22
1.4 BENEFIT - RISK ASSESSMENT	22
2. TRIAL OBJECTIVES AND ENDPOINTS.....	24
2.1 MAIN OBJECTIVES, PRIMARY AND SECONDARY ENDPOINTS	24
2.1.1 Main objectives.....	24
2.1.2 Primary endpoints	24
2.1.3 Secondary endpoints.....	24
	
2.2.2.4 Safety and tolerability	28
3. DESCRIPTION OF DESIGN AND TRIAL POPULATION.....	29
3.1 OVERALL TRIAL DESIGN AND PLAN	29
3.2 DISCUSSION OF TRIAL DESIGN, INCLUDING THE CHOICE OF CONTROL GROUP	30
3.3 SELECTION OF TRIAL POPULATION	30
3.3.1 Main diagnosis for trial entry	30
3.3.2 Inclusion criteria	30
3.3.3 Exclusion criteria	31
3.3.4 Withdrawal of subjects from treatment or assessments	33

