5.2.3 Safety laboratory parameters

For the assessment of laboratory parameters, blood and urine samples will be collected by the trial site at the times indicated in the [Flow Chart](#) after the subjects have fasted for at least 4 h at screening and EOT visits and at least 10 h for all other time points. For retests, at the discretion of the investigator or designee, overnight fasting is not required.

The parameters that will be determined are listed in Tables [5.2.3: 1](#) and [5.2.3: 2](#). Reference ranges will be provided in the ISF, Section 10.

Manual differential white blood cell count or urine sediment examinations will only be performed if there is an abnormality in the automatic blood cell count or in the urinalysis, respectively.

For each Part, SARS-CoV-2 specific test will be conducted at admission on Day – 1, on Day 2, at each admission to the trial site for the 24-h visits (Part 1 only) and at EOT.

[REDACTED]

Table 5.2.3: 1 Routine laboratory tests

Functional lab group	BI test name [comment/abbreviation]	A	B	C
Haematology	Haematocrit	X	X	X
	Haemoglobin	X	X	X
	Red Blood Cell Count/Erythrocytes	X	X	X
	Reticulocytes count	X	X	X
	White Blood Cells/Leucocytes	X	X	X
	Platelet Count/Thrombocytes (quant)	X	X	X
Automatic WBC differential, relative	Neutrophils/Leukocytes; Eosinophils/Leukocytes; Basophils/Leukocytes; Monocytes/Leukocytes; Lymphocytes/Leukocytes	X	X	X
Automatic WBC differential, absolute	Neutrophil, absol.; Eosinophils, absol.; Basophils, absol.; Monocytes, absol.; Lymphocytes, absol.	X	X	X
Manual differential WBC (if automatic differential WBC is abnormal)	Neut. Poly (segs); Neutrophils Bands; Eosinophils/Leukocytes; Basophils/ Leukocytes; Monocytes/ Leukocytes; Lymphocytes/Leukocytes;			
Coagulation	Activated Partial Thromboplastin Time	X	X	X
	Prothrombin time – INR (International Normalization Ratio)	X	X	X
	Fibrinogen	X	X	X
Enzymes	AST [Aspartate transaminase] /GOT, SGOT	X	X	X
	ALT [Alanine transaminase] /GPT, SGPT	X	X	X
	Alkaline Phosphatase	X	X	X
	Gamma-Glutamyl Transferase	X	X	X
	Glutamate Dehydrogenase (GLDH)	X	X	X
	Creatine Kinase [CK]	X	X	X
	Creatine Kinase Isoenzyme MB [only if CK is elevated]	X	X	X
	Lactic Dehydrogenase	X	X	X
	Lipase	X	X	X
	Amylase	X	X	X
PCR	SARS-CoV-2	--	X	X
Hormones	Thyroid Stimulating Hormone	X	--	--
	Free T3 - Triiodothyronine	X	--	--
	Free T4 – Thyroxine	X	--	--
Substrates	Glucose (Plasma)	X	X	X
	Creatinine	X	X	X
	Bilirubin, Total	X	X	X
	Bilirubin, Direct	X	X	X
	Protein, Total	X	X	X

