6. INVESTIGATIONAL PLAN

6.1 VISIT SCHEDULE

Exact times of measurements outside the permitted time windows will be documented. The acceptable time windows for screening and the end of trial examination are provided in the [Flow Chart](#).

Study measurements and assessments scheduled to occur 'before' trial medication administration on Day 1 of each Part are to be performed and completed within a 3 h-period prior to the trial drug administration.

The acceptable deviation from the scheduled time for vital signs, ECG, and laboratory tests will be \pm 30 min on Day 1 of Part 1 and \pm 90 min for the other days in Visit 2.

In Part 1, the planned times for admission, discharge, start and end of the urine and faeces collection intervals are approximate. The procedures are to be performed within a time window of \pm 4 h to the planned time.

In Part 2, the acceptable deviation from the planned times for blood sampling during the ambulatory visits (from Day 30 to Day 62) will be \pm 180 min.

If scheduled in the [Flow Chart](#) at the same time as a meal, blood sampling, vital signs, 12-lead ECG recordings and urine/faeces collection have to be done first. Furthermore, if several measurements including venepuncture are scheduled for the same time, venepuncture should be the last of the measurements due to its inconvenience to the subject and possible influence on physiological parameters.

For planned blood sampling times and urine/faeces collection intervals, refer to the [Flow Chart](#). While these nominal times should be adhered to as closely as possible, the actual sampling times will be recorded and used for the determination of pharmacokinetic parameters. If beginning or end of a urine/faeces collection interval and a blood sample are scheduled for the same time point, urine/faeces collection should be done first, with withdrawal of the blood sample as closely to the planned time point as possible.

If a subject misses an appointment, it will be rescheduled if possible. The relevance of measurements outside the permitted time windows will be assessed no later than at the Report Planning Meeting.

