6.7 BASELINE, TIME WINDOWS AND CALCULATED VISITS

The last non-missing value determined prior to first BI 1358894 administration will be defined as baseline (in both parts).

Time windows are defined in Section 6.1 of the CTP. Adherence to time windows will be checked at the RPM.

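### Part 2 plans its fasted safety laboratory panels on Days 7, 14 and 21 for half an hour after breakfast, so the schedule contradicts its own fasting rule

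*Protocol*

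**What the plan says.** In the Part 2 Flow Chart, the rows for Days 7, 14 and 21 at 08:00 read "Drug administration ¹² B ⁸": the set B panel shares the row with the dose and carries footnote 8 only. That footnote says: "Subjects are to be fasted for at least 10 h before sample is taken". Section 5.2.3 has the same rule in the body text, a fast of "at least 4 h at screening and EOT visits and at least 10 h for all other time points". Footnote 12, attached to the dose on the same rows, says: "A standard continental breakfast will be provided approx. 30 min prior to each daily drug administration from Day 1 to Day 21".

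The PK, urine, ECG and vital signs entries on those rows carry footnote 3, under which "the procedure is to be performed within a time window of 3 h prior to drug administration". The panel does not. Footnote 6 puts meals last, but only when several actions share a time point. Section 6.1 gives laboratory tests a tolerance either way of "90 min for the other days in Visit 2", against half an hour on the Part 1 dosing day.

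SAP Section 6.7 sets the reference value: "The last non-missing value determined prior to first BI 1358894 administration will be defined as baseline". For glucose and lipids that is normally the Day -1 panel. SAP Section 7.8.2 then summarises laboratory values over time and their differences from baseline for the on-treatment phase, and tabulates shifts from baseline to the last on-treatment value.

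**The concern.** The rows for Days 7, 14 and 21 cannot be followed as written: a site that draws at the planned time breaks the fasting footnote attached to that same entry. Set B contains glucose, total cholesterol and triglycerides, and glucose and triglycerides in particular respond to a recent meal. If baseline is fasted, as Section 5.2.3 requires, and these three panels are taken after breakfast, the change from baseline mixes food with drug. Part 2 has one arm and no control, so the summaries cannot separate the two. A food effect could look like a drug effect or hide one. The check that the SAP names is adherence to time windows, and an 08:00 draw passes it.

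**Working it through.** The documents give no figure to reproduce here. The check is clock arithmetic on the Part 2 Flow Chart and Section 6.1.

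**Inputs.** Dose and panel at 08:00 on Days 7, 14 and 21 (Flow Chart). Breakfast about 30 min before the dose (footnote 12). Required fast of at least 10 h (footnote 8, Section 5.2.3). Laboratory window ±90 min (Section 6.1). Eight subjects planned in Part 2.

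**At the planned time.**
- Breakfast: 08:00 − 0:30 = about 07:30.
- Time since food at 08:00: 0.5 h.
- Shortfall: 10 − 0.5 = 9.5 h.

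**Across the window.**
- 08:00 ± 90 min = 06:30 to 09:30, or 180 min.
- Before breakfast: 06:30 to 07:30 = 60 min, or 60/180 = 1/3.
- From breakfast on: 120 min, or 2/3. The last 90 min (08:00 to 09:30) can also be after the dose.
- Does the first hour meet 10 h? The Flow Chart lists no meals on Days 6, 13 and 20. Assuming the last intake is a 20:00 snack, as on the full-profile days, the fast is 10.5 h at 06:30 and 11.5 h at 07:30. It does.

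**Does another rule settle the order?**
- Footnote 3 is not attached to the panel. Adding it would not be enough: 3 h before dosing is 05:00 to 08:00, which still includes 07:30 to 08:00.
- Footnote 6 acts only at a shared time point. Breakfast is at about 07:30 and the panel at 08:00.
- The Section 6.1 rule on completing assessments before dosing covers Day 1 of each Part only.
- Elsewhere Part 2 avoids the clash. Day 1 puts its pre-dose procedures on a 06:00 row ahead of the 07:30 breakfast row. Day 27 lists breakfast on the panel's own row, so footnote 6 puts the panel first.

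**Reach.**
- Scheduled on-treatment panels after the first dose in Part 2: Days 7, 14, 21 and 27. Three of the four are exposed, or 3 × 8 = 24 planned draws.
- End of the Part 2 on-treatment phase (SAP Table 6.1: 2): 480 h + 14 × 24 h = 480 + 336 = 816 h. Day 27 is at 624 h, so it is normally the last on-treatment value and supplies the shift table. It is drawn before breakfast.
- Part 1: the Day 8 and Day 15 panels carry the fasting footnote, and Day -1 falls under Section 5.2.3. The on-treatment phase ends, exclusively, at 14 × 24 = 336 h, and Day 15 is planned at 336 h, so it lies outside the on-treatment summaries anyway.
- Day -1 at 11:00: a 10 h fast means no food after 01:00, which is feasible and already required.

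**The case against.** The strongest reply is that all the stated rules can be met together. The window and the fasting rule both apply, so a compliant draw falls between 06:30 and 07:30. Clock times in the Flow Chart are labelled approximate, and the other procedures on the row are done before dosing, so a pre-breakfast draw is workable. The laboratory analysis is descriptive, clinical significance is judged by the investigator, and protocol deviations are reviewed at the Report Planning Meeting. This stands in part. Fed samples are a risk, not a certainty, and the two-thirds share of the window is not a probability that a sample is fed. But compliance then requires departing from the planned time, and nothing in the schedule tells the site to do so.

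A reader might also infer more than the documents support.
- **That the baseline is non-fasted or undefined.** The Day -1 panel has no fasting footnote in either Flow Chart. Section 5.2.3 nevertheless requires 10 h at every time point other than screening and end of trial, so this is a missing cross-reference. A non-fasted baseline would be a site deviation, not something the protocol instructs.
- **That Part 1 is affected.** Its panels show no contradiction.
- **That the Part 2 shift table is distorted.** It normally rests on Day 27, which precedes breakfast.

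**Conclusion.** The contradiction is real, but its consequence is small. On Days 7, 14 and 21 of Part 2, the planned panel time, footnote 8 and footnote 12 cannot all be followed: a draw at the planned time is 9.5 h short of the required fast, and only 60 of the 180 permitted minutes can comply. What is exposed is the descriptive summary of values and changes from baseline for food-sensitive analytes at those three visits, in up to eight subjects. If Day 27 is missing, Day 21 could become the last on-treatment value and the problem would then reach the shift table for that subject. No primary or secondary endpoint is touched.

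The size of any bias cannot be taken from the documents, which give no food effect for these analytes. As illustration only, if post-breakfast triglycerides were 10% to 50% above fasted values (an assumption), zero drug effect would appear as +10% to +50% from a fasted baseline. The claim that the first hour of the window complies rests on the assumed 20:00 last intake.

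**What to change.** Reconcile the entries by moving the set B panels on Days 7, 14 and 21 of Part 2 to their own row before breakfast. Give them a window that ends at breakfast and starts no earlier than 10 h after the last evening intake. With the assumed 20:00 snack that is 20:00 + 10 h = 06:00, so 06:00 to 07:30. Both limits matter: a 06:00 row that kept the full 90 min on its early side would allow draws from 04:30, only 8.5 h after that snack. Section 6.1 needs a matching exception, so the edit is not confined to the Flow Chart.

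As a minor alignment, attach the fasting footnote to the Day -1 panel in both Flow Charts to match Section 5.2.3.

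The cost is a slightly earlier and narrower sampling slot on three mornings. The number of samples, the dosing and the meals stay as they are.

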$Ae_{urine, 0-t_2}$	Amount of analyte eliminated in urine from time 0 to the last quantifiable timepoint
$AUC_{0-\infty}$	Area under the concentration-time curve of the analyte in plasma over the time interval from 0 extrapolated to infinity
$\%AUC_{t_2-\infty}$	Percentage of $AUC_{0-\infty}$ obtained by extrapolation
$AUC_{t_1-t_2}$	Area under the concentration-time curve of the analyte in plasma over the time interval t_1 to t_2
$AUC_{\tau,ss}$	Area under the concentration-time curve of the analyte in plasma at steady state over a uniform dosing interval τ
AUC_{0-t_2}	Area under the concentration-time curve of the analyte in plasma over the time interval from 0 to the last quantifiable data point
AUC_{0-24}	Area under the concentration-time curve of the analyte in plasma over the time interval from 0 to 24 h
AUC_{0-72}	Area under the concentration-time curve of the analyte in plasma over the time interval from 0 to 72 h
BCRP	Breast cancer resistance protein
BI	Boehringer Ingelheim
BMI	Body mass index (weight divided by height squared)
BP	Blood pressure
BPD	Borderline Personality Disorder
CA	Competent authority
CI	Confidence interval
CL/F	Apparent clearance of the analyte in plasma after extravascular administration
CL_R, t_1-t_2	Renal clearance of the analyte in plasma from the time point t_1 to t_2
C_{max}	Maximum measured concentration of the analyte in plasma
$C_{max,ss}$	Maximum measured concentration of the analyte in plasma at steady-state over a uniform dosing interval τ
CRF	Case Report Form, paper or electronic (sometimes referred to as 'eCRF')
CTM	Clinical Trial Manager
CTP	Clinical trial protocol

Proprietary confidential information © 2020 Boehringer Ingelheim International GmbH or one or more of its affiliated companies

CTR	Clinical trial report
Cum Ae	Cumulative recovery of [¹⁴ C]-radioactivity
Cum %Ae	Cumulative recovery of [¹⁴ C]-radioactivity expressed as a percentage of the dose
CYP3A4	Cytochrome P450 3A4
DG	Dose Group
DILI	Drug induced liver injury
ECG	Electrocardiogram
eCRF	Electronic case report form
eDC	Electronic data capture
EDTA	Ethylenediaminetetraacetic acid
EoTrial	End of trial
EudraCT	European Clinical Trials Database
F	Absolute bioavailability factor
fe _{faeces, t₁-t₂}}	Fraction of administered drug excreted unchanged in urine over the time interval from t ₁ to t ₂
fe _{urine, t₁-t₂}}	Fraction of administered drug excreted unchanged in the faeces over the time interval from t ₁ to t ₂
FIM	First-in-Man
FU	Follow-up
GCP	Good Clinical Practice
GI	Gastro-intestinal
HR	Heart rate
IB	Investigator's brochure
IEC	Independent Ethics Committee
iPD	Important protocol deviation
IRB	Institutional Review Board
ISF	Investigator site file
λ _z	Terminal rate constant of the analyte in plasma
LC-MS/MS	Liquid chromatography with tandem mass spectrometry
LLOQ	Lower limit of quantification
MDA	Methylenedioxymphetamine
MDD	Major Depressive Disorder
MDMA	Methylenedioxymethamphetamine
MedDRA	Medical Dictionary for Regulatory Activities
MRD	Multiple-rising dose
MRT _{ex}	Mean residence time of the analyte in the body, extravascular
PCR	Polymerase chain reaction
PD	Pharmacodynamic(s)

Proprietary confidential information © 2020 Boehringer Ingelheim International GmbH or one or more of its affiliated companies

PK	Pharmacokinetic(s)
PKS	Pharmacokinetic set
PR	Pulse rate
QD	Once daily
QT	Time between start of the Q-wave and the end of the T-wave in an electrocardiogram
QTc	QT interval corrected for heart rate using the method of Fridericia (QTcF) or Bazett (QTcB)
REP	Residual effect period
SAE	Serious adverse event
SCR	Screening
SOP	Standard operating procedure
SRD	Single-rising dose
ss	(at) steady state
SUSAR	Suspected unexpected serious adverse reaction
T	Test product or treatment
TMF	Trial master file
$t_{1/2}$	Terminal half-life of the analyte in plasma
t_{\max}	Time from (last) dosing to the maximum measured concentration of the analyte in plasma
TS	Treated set
t_z	Time of last measurable concentration of the analyte in plasma
TSAP	Trial statistical analysis plan
ULN	Upper limit of normal
V_z	Apparent volume of distribution during the terminal phase after intravascular administration
V_z/F	Apparent volume of distribution during the terminal phase after extravascular administration
XTC	Ecstasy

1. INTRODUCTION

Boehringer Ingelheim (BI) is developing BI 1358894, an oral, small-molecule inhibitor of a transient receptor potential cation channel, subfamily C, members 4 and 5 (TRPC 4/5) for major depressive disorder (MDD) and borderline personality disorder (BPD). BI 1358894 has been characterised to be an inhibitor of P-glycoprotein (P-gp), Breast cancer resistance protein (BCRP) and of the Organic anion transporting polypeptides (OATP) 1B1 and 1B3 in-vitro. This trial should investigate the basic pharmacokinetics, excretion pathways and metabolism of BI 1358894 and its metabolites.

1.1 MEDICAL BACKGROUND

Major depressive disorder is a debilitating disease characterised by low mood and often by low self-esteem, low energy, and a loss of interest. It can strongly impact a person's life and health, including significantly increased risk of suicidality, and is difficult to treat, even with systematic antidepressant strategies. In the National Institute of Mental Health funded STAR*D trial of >4000 patients with nonpsychotic depression, about 30% of the patients did not reach remission after 4 different medications [[P06-11895](#)] and continued to experience residual symptoms [[R16-5475](#)] that significantly impacted the patients' quality of life [[R06-2872](#)]. When monotherapy is insufficient, clinicians employ different augmentation strategies including add-on treatment with lithium or atypical antipsychotics. When augmentation strategies also fail, convulsive therapies such as electro-convulsive therapy may be used.

Borderline personality disorder (BPD) is a chronic mental disorder with an estimated prevalence of around 2% in the general community [[R16-5476](#)] and severely impaired quality of life [[R16-5474](#)]. The main symptom clusters of BPD include impulsive-behavioural dyscontrol, cognitive-perceptual symptoms, disturbed interpersonal relations, and affective instability. Patients with BPD have high rates of deliberate self-harm and a rate of completed suicide that is 50 times higher than in the general population [[R16-5477](#)]. Even the presence of a single diagnostic feature of BPD is predictive for poor functioning and psychiatric illness burden [[R16-5483](#)]. Treatment guidelines recommend psychotherapy as the mainstay of treatment, but pharmacotherapy is commonly used as an adjunctive, symptom-targeted component of treatment. However, no drug is approved for the treatment of BPD.

TRPC4 and TRPC5 form ion channels that are involved in the regulation of neuronal excitability. They are most highly expressed in the amygdala, frontal cortex, hippocampus, and hypothalamus [[R15-3888](#), [R16-5350](#)], which are involved in modulation and processing of emotion and affect. Pre-clinically, treatment with BI 1358894 has shown diminished fear and anxiety and increased social interaction without impairing other brain functions such as learning and memory behaviours.

It is hypothesized that in patients with affective disorders, an overactive amygdala is a major contributor to attentional bias to negative stimuli, pessimistic thoughts, and anxiety [[R16-5473](#)] and there is growing evidence supporting the role of amygdala in the emotion processing disturbances observed in patients with BPD [[R16-5472](#)]. Therefore, treatment with BI 1358894 has the potential to improve affective symptoms and emotion control in patients with MDD and BPD.

